***Not Applicable per Protocol Amendment 04.**

Endpoint	Statistical Analysis Methods

OS in Arm A vs Arm C and in Arm B vs Arm C OS is defined as the time between the date of randomization and the date of death due to any cause. For participants still alive, OS is censored at the last date the participant is known to be alive.
	
OS will be analyzed in the all randomized participants population. The same analyses as described for EFS analyses will be performed for OS. The hypothesis testing will only be performed if the higher hierarchical endpoints are met, as described in the SAP.

pCR in Arm A vs Arm B Same definition as the corresponding primary endpoint.
	
pCR rates and corresponding 95% exact CIs will be calculated using the Clopper Pearson method for each treatment group in the all randomized participants population. Associated odds ratio and estimate of the difference with 95% CI will be calculated.

EFS in Arm A vs Arm B Same definition as the corresponding primary endpoint
	
The EFS curves for each randomized arm will be estimated using the Kaplan-Meier (KM) product-limit method. In addition, EFS rates at specific time points will be estimated using KM estimates on the EFS curve for each randomized arm. Associated 2-sided 95% CIs will be calculated using the Greenwood formula (using log-log transformation). The hazard ratio and the corresponding 95% will be estimated in a stratified Cox proportional hazards model using the randomized arm as a single covariate.

[REDACTED]
	
[REDACTED]

[REDACTED]
	
[REDACTED]

The stratification factors for analysis are the following:

- Clinical Stage (T2N0 vs T3-T4aN0 vs T1-T4aN1)
- PD-L1 status ($\geq 1\%$ vs $< 1\%$ /indeterminate)

Text related to alpha spending and hierarchical testing in the following paragraphs is not applicable in Protocol Amendment 04. The overall 2-sided alpha for this study is 0.05, which is split with 0.001 for pCR and 0.049 for EFS for both Arm A vs Arm C comparison.

[figure not shown]
No formal powered comparison of Arm A versus Arm B is planned, therefore, it may not be possible to draw any conclusion from the trial results about the superiority of Arm A compared to Arm B.

To control the type I error rate, the following hierarchical testing approach will be implemented:

- 1) pCR: A vs C will be first tested at 0.001 alpha (two-sided)
- 2) pCR: B vs C will be tested at 0.001 alpha (two-sided) if i. was significant
- 3) EFS: A vs C will be tested at 0.049 (or 0.05 if ii. was significant) alpha (two-sided)
- 4) EFS: B vs C will be tested if iii. was significant and with the same alpha (two-sided)
- 5) OS: A vs C will be tested if iv. was significant and with the same alpha (two-sided)
- 6) OS: B vs C will be tested if v. was significant and with the same alpha (two-sided)

This approach has a graphical representation, which is illustrated in Figure 10.3-1.

Figure 10.3-1: *Not Applicable per Protocol Amendment 04. Graphical Representation of the Statistical Testing Approach

Number in the circle: initial alpha allocation
Arrows: if comparison is significant, alpha is passed to the next comparison with corresponding allocation rate

Given EFS and OS endpoints are tested hierarchically using a group sequential approach, the overall hierarchical testing approach will be used where each endpoint/comparison will have its own specific Lan-DeMets alpha spending function with the O'Brien-Fleming type of boundaries.⁷³ Additional details around the interim analysis schedule is provided in [Section 10.3.3](#).

10.3.1 Safety Analyses

All safety analyses will be performed on the all treated participants population.

Table 10.3.1-1: Safety Analyses

Endpoint	Statistical Analysis Methods
Secondary	Descriptive statistics of safety will be presented using NCI CTCAE version 5.0 by treatment group. All on-study AEs, treatment-related AEs, SAEs, and treatment-related SAEs will be tabulated using worst grade per NCI CTCAE v 5.0 criteria by system organ class and

Table 10.3.1-1: Safety Analyses

Endpoint	Statistical Analysis Methods
	preferred term. On-study laboratory parameters including hematology, chemistry, liver function, and renal function will be summarized using worst grade NCI CTCAE v 5.0 criteria. Additional safety analyses will be described in the statistical analysis plan finalized before first database lock.

[Redacted content]

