		Within 14 Days Before Surgery	60-90 Days Post- surgery	Follow-up Visits 1 and 2	*Not applicable per Protocol Amendment 04. Survival Follow-up Visits ^b	
Study Treatment^c						
Randomize	X					Radical Cystectomy must occur within 6 weeks from randomization.
Safety Assessments						
Targeted Physical Examination, Measurements, Vital Signs, and Performance Status		X	X	X		Vital Signs: BP, Heart Rate, and Temperature Weight ECOG Performance Status
Concomitant Medication Use	Continuously					Record at each visit.
Subsequent Anti-cancer Therapy ^d				X	X	Per protocol amendment 04, the following will no longer be collected after 100 days of follow-up: Collect every 3 months at Survival Visits until death, lost to follow-up, withdrawal of study consent, or up to 5 years. May be performed by phone contact or office visit. Include documentation of additional subsequent cancer therapy details

Table 2-5: Study Assessments - Arm C

***Per Protocol Amendment 04, participants will discontinue from the study following one recurrence update and survival status update.**

Procedure	Pre-surgery	Pre-surgery	Post-surgery	Follow-up ^a		Notes
		Within 14 Days Before Surgery	60-90 Days Post- surgery	Follow-up Visits 1 and 2	*Not applicable per Protocol Amendment 04. Survival Follow-up Visits ^b	
						such as regimen, setting of the regimen, line of therapy, start date and end date of each regimen, and date of progression to subsequent anti-cancer therapies will be collected.
SAE/AE Assessment	Continuously until 100 days from RC. Participants will be followed for all SAEs, non-serious AEs of special interest (as defined in Section 9.8), and all AEs (SAEs and non-serious AEs) associated with confirmed or suspected SARS-CoV-2 infection until resolution, the condition stabilizes, the event is otherwise explained, the event is deemed irreversible, the participant is lost to follow-up (as defined in Section 8.3), or for suspected cases, until SARS-CoV-2 infection is ruled-out.					
Efficacy Assessments						
*Not applicable per Protocol Amendment 04. Submission of Tissue for Pathologic Complete Response (pCR)	*Not applicable per Protocol Amendment 04. Please review details for specimen collection and submission in the Laboratory Manual.					

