7 TREATMENT

Study treatment is defined as any investigational treatment(s), marketed product(s), placebo or medical device intended to be administered to a study participant according to the study randomization or treatment allocation.

Study treatment includes both Investigational [Medicinal] Product (IP/IMP) and Non-investigational [Medicinal] Product (Non-IP/Non-IMP) and can consist of the following:

- Nivolumab Solution for Injection
- **Not applicable per Protocol Amendment 04.** Bempegaldesleukin (NKTR-214) Powder for Solution for Injection

An investigational product, also known as investigational medicinal product in some regions, is defined a pharmaceutical form of an active substance or placebo being tested or used as a reference in a clinical study, including products already with a marketing authorization but used or assembled (formulated or packaged) differently than the authorized form, or used for an unauthorized indication, or when used to gain further information about the authorized form.

Other medications used as support or escape medication for preventative, diagnostic, or therapeutic reasons, as components of the SOC for a given diagnosis, may be considered as non-investigational products.

Per Protocol Amendment 04, all participants receiving bempegaldesleukin plus nivolumab are required to discontinue bempegaldesleukin and may continue nivolumab monotherapy. Participants in Arm A and Arm B will receive nivolumab monotherapy 360 mg IV Q3W for the remainder of the study treatment period.

Table 7-1: Study Treatments for CA045009/18-214-13

Product Description / Class and Dosage Form	Potency	IP/Non-IMP	Blinded or Open Label	Packaging / Appearance	Storage Conditions (per label)

*Not applicable per Protocol Amendment 04
 
Bempegaldesleukin (NKTR-214) Powder for Solution for Injection
	0.3 mg, 0.5 mg, or 1 mg of rhIL-2 per vial ^a	IP	Open-label	Vial (one or more vials per carton)	Refer to the label on container and/or pharmacy manual
Nivolumab Solution for Injection ^b	100 mg (10 mg/mL)	IP	Open-label	Vial (multiple vials/carton)	Store at 2°-8°C. Protect from light and freezing.

^a ***Not applicable per Protocol Amendment 04.** Note: For bempegaldesleukin (NKTR-214), IL-2 and rhIL-2 refer to the same molecule.

^b May be labeled as either “BMS-936558-01” or “nivolumab.”

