9.2.1 Time Period and Frequency for Collecting AE and SAE Information

Serious Adverse Drug Reactions section in the IB represent the Reference Safety Information to determine expectedness of SAEs for expedited reporting.

- The collection of non-serious AEs (with the exception of non-serious AEs related to SARS-CoV-2 infection) should begin at initiation of study treatment. All SAEs, and all AEs (SAEs and non-serious AEs) associated with confirmed or suspected SARS-CoV-2 infection must be collected from the date of the participant's written consent until 100 days following discontinuation of dosing.
- All SAEs must be collected from the time of signing the consent, including those thought to be associated with protocol-specified procedures and within 100 days of discontinuation of dosing.
- For participants randomized to treatment and never treated with study drug, SAEs should be collected for 30 days from the date of randomization. For participants in Arm C, SAEs should be collected for 100 days following RC.
- The investigator must report any SAE that occurs after these time periods and that is believed to be related to study drug or protocol-specified procedure, (eg, a follow-up skin biopsy).
- Medical occurrences that begin before the start of study treatment but after obtaining informed consent will be recorded on the appropriate section of the eCRF module.
- All SAEs will be recorded and reported to Sponsor or designee within 24 hours, as indicated in Appendix 3.
- The investigator will submit any updated SAE data to the sponsor or designee within 24 hours of updated information being available.
- CVA (any grade) is considered an AEOSI and should be assessed for seriousness using the standard seriousness definition. However, all CVAs are required to follow the timelines for SAE reporting (eg, 24 hours). CVA management guidelines, provided in [Appendix 7](#), are no longer applicable per Protocol Amendment 04.

Investigators are not obligated to actively seek AEs or SAEs in former study participants. However, if the investigator learns of any SAE, including a death, at any time after a participant has been discharged from the study, and he/she considers the event reasonably related to the study treatment or study participation, the investigator must promptly notify the sponsor.

The method of evaluating, and assessing causality of AEs and SAEs and the procedures for completing and reporting/transmitting SAE reports are provided in Appendix 3.

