9.2.2 Method of Detecting AEs and SAEs

Adverse events can be spontaneously reported or elicited during open-ended questioning, examination, or evaluation of a participant. Care should be taken not to introduce bias when

collecting AE and/or SAEs. Inquiry about specific AEs should be guided by clinical judgement in the context of known AEs, when appropriate for the program or protocol.

All nonserious AEs (not only those deemed to be treatment-related) should be collected continuously during the treatment period and for a minimum of 100 days following discontinuation of adjuvant therapy for Arms A and B and 100 days from RC for Arm C. For participants who do not continue adjuvant therapy in Arms A and B, AEs and/or SAEs should be collected for a period of 100 days following RC.

Every AE must be assessed by the investigator with regard to whether it is considered immune-mediated. For events which are potentially immune-mediated, additional information will be collected on the participant's case report form.

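### Adverse event collection runs longer in Arms A and B than in Arm C, so the worst-grade tables of Section 10.3.1 need an exposure-adjusted or common-window companion before A or B is read against C (minor)

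*Combined protocol and SAP*

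**What the plan says.** **Analysis.** Section 10.3.1 places all safety analyses in the all-treated population and summarizes by treatment group: "All on-study AEs, treatment-related AEs, SAEs, and treatment-related SAEs will be tabulated using worst grade". It leaves additional safety analyses to the SAP. It mentions neither exposure adjustment nor a common window.

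**End of collection.** Section 9.2.2 has non-serious AEs collected through treatment, then "for a minimum of 100 days following discontinuation of adjuvant therapy for Arms A and B and 100 days from RC for Arm C". Where A/B participants do not go on to adjuvant therapy, "AEs and/or SAEs should be collected for a period of 100 days following RC"; the AE row of Table 2-4 gives the same rule for SAEs and non-serious AEs. For Arm C, Table 2-5 says "Continuously until 100 days from RC", and Section 9.2.1 gives the same limit for SAEs.

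**Start of collection.** SAEs are collected from consent. For other events, Section 9.2.1 says: "The collection of non-serious AEs (with the exception of non-serious AEs related to SARS-CoV-2 infection) should begin at initiation of study treatment". Section 7 says: "Study treatment is defined as any investigational treatment(s), marketed product(s), placebo or medical device intended to be administered to a study participant". Arm C has no such product, although Section 5.1 counts RC as part of the study treatment.

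**Population.** The Amendment 04 sentences in the Synopsis and Section 4 put safety in all randomized participants. Section 10.3.1 and the safety rows of Tables 1-1 and 4-1 say all treated. Section 10.3 applies the all-randomized set only to pCR, EFS and OS.

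**The concern.** Safety is one of the objectives that Amendment 04 keeps, and Arm C is the only arm without study drug, so readers will naturally use it as the reference column. A cumulative table counts a participant once if the event occurs at any time while events are being collected. A longer window gives a higher percentage even when the underlying rate is the same. Nothing in the supplied text tells the reader that the columns cover different lengths of time. Later follow-up cannot close the gap, because under Amendment 04 Arm C participants leave the study after the 100-day safety follow-up (Section 5.1). Any remedy has to be in the analysis.

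**Working it through.** **Inputs.** Dosing is every 3 weeks, with 3 neoadjuvant and up to 12 adjuvant cycles (Section 5.1). RC is due within 6 weeks of the last neoadjuvant dose in A/B, or of randomization in C (Section 5.1.2.2). Adjuvant therapy starts 60 to 120 days after RC or, without RC, no sooner than 3 weeks after the last neoadjuvant dose (Section 5.1.2.3). I assume no dose delays and ignore the up to 3 days between randomization and first dose.

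**Reproducing the plan's own figure.** The third neoadjuvant dose falls on day 2 × 21 = 42. The twelfth adjuvant dose comes 11 × 21 = 231 days after the first. The longest course to last dose is 42 + 42 + 120 + 231 = 435 days = 62.1 weeks, against the stated maximum of 62 weeks (434 days). Adding 100 days of safety follow-up to the stated figure gives 534 days.

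**Scheduled windows from randomization.**

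| Path | Days | Ratio to 142 |
|---|---|---|
| Arm C, RC at 6 weeks (longest) | 42 + 100 = 142 | 1.0 |
| A/B, RC at 6 weeks, no adjuvant | 42 + 42 + 100 = 184 | 1.3 |
| A/B, no RC, full adjuvant (earliest start) | 42 + 21 + 231 + 100 = 394 | 2.8 |
| A/B, RC, full adjuvant, shortest | 42 + 0 + 60 + 231 + 100 = 433 | 3.0 |
| A/B, RC, full adjuvant, longest | 434 + 100 = 534 | 3.8 |

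These are scheduled limits, not averages. Many A/B participants will stop earlier, and Arm C participants with RC before day 42 have less than 142 days.

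**Sensitivity to Arm C visit timing.** Table 2-5, footnote a, puts Follow-up Visit 2 about 100 days after the post-surgery visit, which is itself 60 to 90 days after RC. If AEs were in practice captured to that visit, the Arm C window would be up to 42 + 90 + 100 = 232 days and the top ratio 534/232 = 2.3. With the post-surgery visit at 60 days it would be 202 days and 534/202 = 2.6.

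**Illustration.** The documents give no AE rates for this trial. Assume the same constant hazard in both arms and an Arm C percentage p over 142 days. Over T days the percentage is 1 − (1 − p)^(T/142).

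| Assumed p in Arm C | T = 184 | T = 394 | T = 534 |
|---|---|---|---|
| 5% | 6.4% | 13.3% | 17.5% |
| 10% | 12.8% | 25.3% | 32.7% |
| 20% | 25.1% | 46.2% | 56.8% |

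An arm-level percentage averages over all paths, so it would lie between these columns or lower, according to how many participants reach adjuvant therapy.

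**The case against.** The strongest reply is that no planned analysis is wrong. The objective is to assess safety for each arm, 10.3.1 is descriptive, and cumulative burden over the assigned regimen is a legitimate thing to report. That stands, and it limits the point to how columns are read side by side. It also stands that the SAP may already contain exposure-adjusted output, and that a constant hazard is doubtful when every treated Arm C participant has major surgery early in a short window.

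Three stronger readings are tempting, and the documents do not support them.

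- A reader might infer that non-serious AE collection in Arm C starts only at RC, leaving a 100-day window. Section 9.2.1 read with Section 7 allows this. Table 2-5, however, calls for continuous assessment in a schedule that opens at randomization. The start is unclear; a late start is not established.
- A reader might infer that SAE collection in A/B participants without adjuvant therapy stops 100 days after dosing, because Section 9.2.1 describes SAE collection as "including those thought to be associated with protocol-specified procedures and within 100 days of discontinuation of dosing". That sentence is general. Table 2-4 and Section 9.2.2 address this group specifically and anchor it at RC.
- A reader might infer that a day-100 table would be complete for every AE. For non-serious AEs that depends on the unresolved Arm C start.

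**Conclusion.** The point holds as a minor, cheap improvement. Scheduled collection is 1.3 to 3.8 times as long in A/B as in Arm C at its 142-day maximum, so A against C and B against C percentages from the planned tables would partly measure collection time. The top ratio falls to about 2.3 if Arm C events were captured to Follow-up Visit 2 at its latest. Each arm's table and A against B are unaffected. A reader might conclude that 10.3.1 is wrong, or that any excess of events over Arm C is an artefact. Neither follows: no safety comparison or test is planned, and the documents contain no AE rates or actual exposure from which to size the effect. The ratios rest on undelayed scheduled dosing, and the percentages on an assumed equal constant hazard. The population wording is a separate editorial mismatch.

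**What to change.** 1. **Tables.** Keep the cumulative tables. In 10.3.1 or the SAP, add exposure-adjusted incidence by arm and a table of SAEs from randomization to day 100. Include non-serious AEs in the day-100 table only once it is confirmed that Arm C collection starts at randomization.
2. **Footnote.** Give each arm's collection window under the tables, and state when non-serious AE collection starts in Arm C (Table 2-5 against Section 9.2.1).
3. **Minor wording.**
   - In the Amendment 04 sentences of the Synopsis and Section 4, use all treated for safety, to match 10.3.1.
   - Align the general SAE sentence of Section 9.2.1 with Table 2-4 and Section 9.2.2 for A/B participants without adjuvant therapy.
   - Reconcile the 30-day rule with Table 10.2-1. The rule reads "For participants randomized to treatment and never treated with study drug, SAEs should be collected for 30 days from the date of randomization", yet an A/B participant who was never dosed but had RC is in the all-treated set. Until this is settled, that group is an exception to completeness of the day-100 SAE table.
   - Reconcile Arm C visit timing (Table 2-5, footnote a) with the RC + 100 days limit.

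**Cost.** Two tables from data already collected, a footnote and a few wording changes. The downsides are extra output for a terminated trial and person-time rates that assume a roughly constant hazard. The day-100 table discards later adjuvant events. It also covers less time after surgery in A/B: after three neoadjuvant cycles RC falls on day 42 to 84, leaving 58 to 16 days, against at least 100 − 42 = 58 days in Arm C.

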10.3.3 Interim Analyses

Per Protocol Amendment 04 this section is not applicable.

Several interim analyses are planned for efficacy. [Table 10.3.3-1](#) gives an overview of interim analyses purpose and timing.

Table 10.3.3-1: Interim Analyses Schedule

***Not Applicable per Protocol Amendment 04.**

Analysis	Purpose	Analysis Trigger	Projected Timing^a	Number of Participants/Events
Final pCR Interim EFS 1	Demonstrate significant improvement in pCR and EFS	All randomized participants who underwent RC have pCR evaluation	~47 months	pCR: all randomized participants (~360 in Arms A and C) EFS: ~101 events (Arms A and C)
Interim EFS 2 Interim OS 1	Demonstrate significant improvement in EFS and OS	~133 EFS events in arms A and C	~56 months	EFS: ~133 events (Arms A and C) OS: ~109 events (Arms A and C)
Final EFS Interim OS 2	Demonstrate significant improvement in EFS and OS	~156 EFS events in arms A and C	~65 months	EFS: ~156 events (Arms A and C) OS: ~131 events (Arms A and C)
Final OS	Demonstrate significant improvement in OS	~156 OS events in arms A and C	~86 months	OS: ~156 events (Arms A and C)

^a Approximate projected timing from the start of randomization

10.3.4 Interim Analyses for EFS

Per Protocol Amendment 04 this section is not applicable.

Two interim analyses for efficacy of EFS are planned. The first will take place at the time of final pCR analysis (approximately after 101 EFS events in Arms A and C). The second interim analysis will take place when approximately 85% of the total number of events have occurred (approximately 133 events in Arms A and C). Details are provided in [Section 10.3.3](#). There is no futility analysis for EFS.

10.3.5 Interim Analyses for OS

Per Protocol Amendment 04 this section is not applicable.

Two interim efficacy analyses of OS are planned. The first will take place at the time of EFS interim analysis 2 (approximately after 133 EFS events in Arms A and C). The second OS interim analysis will take place at the time of final EFS analysis. In case EFS reaches significance at an interim analysis, the subsequent OS analyses timing will be based on the OS number of events (approximately 109 OS events in Arms A and C for interim 1 and 131 OS events in Arms A and C for interim 2). There is no futility analysis for OS.

These interim comparisons for EFS and OS will allow for early formal testing for superiority, and the boundaries for declaring superiority will be derived based on the actual number of events using

Lan-DeMets spending function with O'Brien and Fleming type of boundary in EAST version 6 based on the information fraction observed.

An independent statistician external to BMS will perform interim analyses (in conjunction with a review by the Data Monitoring Committee). The SAP will further describe the planned interim analyses.

